#### 4.1.2.2 Secondary Definition of Progression Free Survival (Irrespective of Subsequent Therapy)

[figure not shown]
The secondary definition of PFS (ITT definition) is defined as the time between the date of randomization and the date of first documented tumor progression, based on BICR assessments (per RECIST v1.1 criteria), or death due to any cause, whichever occurs first.

The following censoring rules will be applied for the secondary definition of PFS:

- Subjects who did not progress or die will be censored on the date of their last evaluable tumor assessment.
- Subjects who did not have any on study tumor assessments and did not die will be censored on their date of randomization.

Censoring rules for the secondary definition of PFS (ITT definition) are presented in Figure 4.1.2.2-1 and in Table 4.1.2.2-1.

Figure 4.1.2.2-1: PFS Secondary Definition

**Table 4.1.2.2-1: Censoring Scheme for Secondary Definition of PFS**

Situation	Date of Progression of Censoring	Outcome
No baseline tumor assessment	Date of randomization	Censored
No on-study tumor assessments and no death	Date of randomization	Censored
Documented progression per RECIST v1.1	Date of first documented progression per RECIST v1.1 criteria (excludes clinical progression)	Progressed
No progression and no death	Date of last evaluable tumor assessment	Censored
Death without progression per RECIST v1.1	Date of death	Progressed

## **4.2 Secondary Endpoints**

### **4.2.1 For Nivo + Chemo versus Chemo**

#### **4.2.1.1 Overall Survival**

Secondary objectives are the comparison of OS between nivo+chemo and chemo in PD-L1 CPS  $\geq 1$  subjects and in all randomized subjects. OS will also be evaluated for subjects with CPS  $\geq 10$ . Overall survival is as defined in [Section 4.1.1](#).

#### **4.2.1.2 Progression-Free Survival**

Secondary objectives are the evaluation of PFS per BICR for nivo+chemo and chemo in PD-L1 CPS  $\geq 1$  subjects, CPS  $\geq 10$  subjects and in all randomized subjects. Progression free survival is as defined in [Section 4.1.2](#).

#### **4.2.1.3 Objective Response Rate**

Objective Response Rate (ORR) is defined as the number of randomized subjects who achieve a best overall response of confirmed complete response (CR) or confirmed partial response (PR) based on BICR assessment (using RECISTS v1.1) divided by the number of randomized subjects.

Best Overall Response (BOR) is defined as the best response, as determined by the BICR, recorded between the date of randomization and the date of objectively documented progression per RECIST v1.1 criteria or the date of subsequent anti-cancer therapy (including all systemic therapies, surgery with reason of tumor resection palliative or tumor resection curative, radiotherapy with reason curative or palliative), whichever occurs first. For subjects without documented progression or subsequent therapy, all available response designations will contribute to the BOR determination.

ORR will be evaluated for nivo + chemo and chemo in PD-L1 CPS  $\geq 10, 5, 1$  or all randomized subjects.

## **4.2.2 For Nivo + Ipi versus Chemo.**

### **4.2.2.1 Overall Survival**

Secondary objectives are the comparison of OS between nivo+ipi and chemo in PD-L1 CPS  $\geq 5$  subjects and in all randomized subjects. OS will also be evaluated for subjects with CPS  $\geq 10$  and CPS  $\geq 1$  subjects. Overall survival is as defined in [Section 4.1.1](#).

### **4.2.2.2 Progression Free Survival**

Secondary objectives are the evaluation of PFS per BICR for nivo+ipi and chemo in PD-L1 CPS  $\geq 10$ , CPS  $\geq 5$ , CPS  $\geq 1$  and in all randomized subjects. Progression free survival is as defined in [Section 4.1.2](#).

### **4.2.2.3 Objective Response Rate**

Secondary objectives are the evaluation of ORR per BICR for nivo+ipi and chemo in PD-L1 CPS  $\geq 10$ , CPS  $\geq 5$ , CPS  $\geq 1$  and in all randomized subjects. Objective response rate is as defined in [Section 4.2.1.3](#).

### **4.2.2.4 Time to Symptom Deterioration**

Time to symptom deterioration is defined as the time from randomization until a clinically meaningful decline from baseline in GaCS score. A clinically meaningful deterioration is defined as a reduction of 8.2 points in the GaCS score. Only events before treatment discontinuation will be taken into account: patients who do not deteriorate before treatment discontinuation will be censored at the time of their last on-treatment GaCS assessment. Those who have no GaCS assessments after randomization and those who were never treated will be censored on the date of randomization. For more details on the GaCS scale, see [Section 4.3.3](#). Secondary objectives are the comparison of TTSD between nivo+ipi and chemo in PD-L1 CPS  $\geq 5$  subjects and all randomized subjects.

## **4.3 Exploratory Endpoints**

### **4.3.1 Efficacy Exploratory Endpoints**

All the following exploratory endpoints may be explored on the different CPS population (ie, CPS  $\geq 10$ , CPS  $\geq 5$ , CPS  $\geq 1$  and all randomized).

#### **Progression-Free Survival**

Progression-free Survival as assessed by investigator is defined similarly as the corresponding endpoints as assessed by BICR.

#### **Objective Response Rate**

Objective Response Rate (as assessed by investigator) is defined similarly as the corresponding endpoint as assessed by BICR.

#### **Duration of Response**

Duration of response is defined as the time between the date of first confirmed documented response (CR or PR) and the date of the first documented tumor progression as determined by the

BICR or investigator (per RECIST v1.1 criteria) or death due to any cause, whichever occurs first. Censoring rules for DOR follow the censoring rules for PFS primary definition.

### **Durable Response rate**

Durable Response Rate is defined as the number of subjects with confirmed documented response (CR or PR) as determined by the BICR or investigator (per RECIST v1.1 criteria) whose response lasted for at least 6 months, divided by the number of randomized subjects.

### **Survival Rate**

OS rates at fixed time points (eg, 18, 14, 16 months, depending on the minimum follow-up) are defined as the probability that a subject is alive at time  $T$  following randomization. Overall survival rates at other timepoints are defined similarly.

### **PFS2/TSST**

PFS on next-line therapy (PFS2) is defined as the time from randomization to objectively documented progression, per investigator assessment, on the start of the next line of therapy or the start of the second next line therapy or to death from any cause, whichever occurs first. Subjects who are alive and without progression on the next line of therapy will be censored at last known alive date.

The following censoring rules will be applied for PFS2:

- Subjects who did not receive subsequent anti-cancer therapy (ie, next-line therapy):
  - Subjects who died, the death date is the event date;
  - Else the subject's PFS2 is censored at the last known alive date.
- Subjects who received subsequent anti-cancer therapy (ie, next-line therapy):
  - Subjects who had a disease progression after the start of subsequent next line anti-cancer therapy, this disease progression date is the event date;
  - Else if a subject died or start of second next line therapy, the date of min (death, start date of second next line therapy) is the event date;
  - Else the subject's PFS2 is censored at the last known alive date.

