Dispense Study Treatment	X	X	X	First dose to be administered within 3 calendar days after randomization. XELOX dose schedule: see Table 4.6.1-1. Subsequent	
				XELOX doses may be administered within dosing windows per package insert or local standard.	
				FOLFOX dose schedule: see Table 4.6.1-2. Subsequent FOLFOX doses may be administered within dosing windows per package insert or local standard.	
				Vials may be assigned up to 3 calendar days prior to every dose date.	

Table 5.1-5: Follow-Up Procedural Outline - All Subjects (CA209649)					
Procedure	Follow-up Visits 1 and 2 FU1: 30 days (± 7 days) after last dose FU2: 84 days (± 7 days) after FU1	Survival Follow-Up Visits every 3 months (± 14 days) from FU2	Notes		
Safety Assessments					
Physical Examination	X				
Adverse Events Assessment	X		Assessed using NCI CTCAE v.4		
Review of Subsequent Cancer Therapy	X	X	Additional subsequent cancer therapy details such as regimen, setting of the regimen, line of therapy, start date and end date of each regimen, best response to the regimen and date of progression after second line therapy will be collected.		
			The above information will be also collected during survival follow up period		
Review of Concomitant Medications	X				
Laboratory Tests	See Note		Include CBC w/differential, ALT, AST, total bilirubin, BUN or serum urea level, creatinine, Ca, Na, K, Cl, LDH and glucose.		
			If there are ongoing AE, monthly lab tests will be conducted till FU2.		
Pregnancy Test (WOCBP only)	See Note		Serum or urine, only for FU1, unless testing is required for a longer period, per local regulations.		
Efficacy Assessments					
Tumor Imaging Assessment	See Note	See Note	For subjects who discontinue study drug for reasons other than PD, follow-up scans should be performed every 6 weeks (± 7 days) up to and including Week 48, then every 12 weeks (± 7 days) until PD, lost to follow-up, or withdrawal of consent. Radiographic assessments should not be delayed until follow-up visits 1 & 2.		

Table 5.1-5: Follow-U	p Procedural Outline - A	all Subjects (CA209649)	
Procedure	Follow-up Visits 1 and 2 FU1: 30 days (± 7 days) after last dose FU2: 84 days (± 7 days) after FU1	Survival Follow-Up Visits every 3 months (± 14 days) from FU2	Notes
			CT/MRI scan of chest, abdomen, pelvis, and any clinically indicated sites.
			Use same imaging method as was used at screening/baseline.
Outcomes Research Assessments	·		
GaCS from the FACT-Ga	X		

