8.3.3 Exploratory Measures

- PFS by investigator and ORR by investigator are defined the same way as PFS by BICR and ORR by BICR, except that only tumor assessments by investigators will be taken into account.
- Duration of Response (DOR) (as assessed by BICR and as assessed by investigator) is defined as the time between the date of first documented response (CR or PR) to the date of the first disease progression, per RECIST 1.1 or death due to any cause, whichever occurs first. For subjects who neither progress nor die, the duration of objective response will be censored at the same time they were censored for the primary definition of PFS.

• Durable Response Rate (DRR) (as assessed by BICR and as assessed by investigator) is defined as the number of subjects with objective response whose response lasted for at least 6 months, divided by the number of randomized subjects for each treatment group.

- Overall survival rate at 18, 24, and 36 months is defined as the probability that a subject is alive at 18, 24, and 36 months, respectively, following randomization.
- PFS2/TSST is defined as the time from randomization to the date of investigator-defined documented second objective disease progression or start of second subsequent line therapy or death due to any cause, whichever comes first. Clinical deterioration will not be considered as progression. Details for censoring will be provided in the SAP
- Safety and tolerability objective will be measured by the incidence of adverse events (AEs), serious adverse events (SAEs), deaths, and laboratory abnormalities.
- PK will be measured using serum concentration-time data.

Assessments for other exploratory endpoints are discussed, including biomarker analysis (Section 5.6), immunogenicity (Section 5.5.1), and outcomes research (Section 5.7). Corresponding endpoints will be detailed in the statistical analysis plan(s) (SAP[s]).

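### The SAP's PFS2 derivation ignores a second next-line therapy that starts before a recorded progression, so some PFS2 times come out longer than the definition allows

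*SAP*

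**What the plan says.** The definition of PFS2 in SAP 4.3.1 (PFS2/TSST) runs from randomization to investigator-assessed progression on next-line therapy, "or the start of the second next line therapy or to death from any cause, whichever occurs first". Protocol 8.3.3 gives the same structure: second objective progression, or "start of second subsequent line therapy or death due to any cause, whichever comes first". The protocol adds that "Clinical deterioration will not be considered as progression" and leaves the detail to the other document: "Details for censoring will be provided in the SAP". The SAP rules are therefore the operative ones.

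Those rules are a sequence of steps. For subjects who received next-line therapy, the first step is: "Subjects who had a disease progression after the start of subsequent next line anti-cancer therapy, this disease progression date is the event date". The second step is reached only when the first does not apply. It opens with "Else if a subject died or start of second next line therapy" and takes whichever of those two dates is earlier. Subjects who meet neither step are censored at the date last known alive.

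PFS2 is listed as exploratory for both comparisons. SAP 7.5.2.10 and 7.5.3.9 plan Kaplan-Meier medians with 95% confidence intervals, curves, and a by-subject listing of PFS and PFS2.

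**The concern.** The definition asks for the earliest of three dates, but the rules never compare the progression date with the start of second next-line therapy. Once a subject has any progression after next-line therapy began, that date is used, even if a further line had already started. The first step has no upper limit in time, so the progression it picks up may have occurred on the later line.

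This ordering can arise. A subject whose treatment is changed for toxicity, or for clinical worsening that does not count as progression, starts the second next line without a qualifying event. Such a subject should have a PFS2 event on the switch date and instead gets a later one. In an open-label trial, if early switching were more common in one arm, that arm's PFS2 curve would be flattered relative to the other.

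**Working it through.** No event count, power or significance level is attached to PFS2, so there is no planned figure to reproduce. The check compares the two rules directly.

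**Inputs.** For a subject who received next-line therapy, let P be the progression date after next-line start, T the start of second next-line therapy, and D the date of death. Each is infinite if it did not occur. P and T cannot be later than D.

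**Definition** (SAP 4.3.1 lead text; Protocol 8.3.3): M = min(P, T, D).

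**Derivation rules** (SAP 4.3.1 steps): R = P if P is finite; otherwise R = min(T, D).

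**Comparison.**
- If P is infinite, R = min(T, D) = M. The rules agree.
- If P is finite, D is not earlier than P, so M = min(P, T) while R = P. The rules agree when T is not before P. When T is before P, R exceeds M by P − T.
- Either version records an event exactly when at least one of the three dates is finite, so the event/censoring flag is the same.

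**Cases in months**, with next-line therapy already started and the date last known alive at month 20 where needed:

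| Pattern | SAP steps | Definition |
|---|---|---|
| P = 9, T = 10, D = 15 | 9 | 9 |
| T = 9, no P, D = 15 | 9 | 9 |
| P = 9 only | 9 | 9 |
| T = 9, P = 12, D = 15 | 12 | 9 |
| T = 9, P = 12, alive | 12 | 9 |
| no event | 20, censored | 20, censored |

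For T = 10 and P = 14, the excess is 14 − 10 = 4 months.

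Applying both rules to 200,000 random date patterns gave the same picture. The SAP steps were never earlier than the definition, the event flag never differed, and the SAP date was later only when T preceded a recorded P. That happened in 16,652 patterns, but the frequency reflects arbitrary inputs and says nothing about the trial.

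**Data available.** The follow-up schedule in Protocol 5.1 collects start and end dates of each subsequent regimen, and "date of progression after second line therapy will be collected". The dates needed for the correct rule are already captured.

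**The case against.** The strongest counter-argument is that the steps should be read under the definition above them. If the first step means progression while on the next line, before the second next line begins, an early switcher passes to the second step and gets the right date. The sentence closing the definition, which speaks of subjects without progression on the next line, gives this reading some support. The first step does not say it, however: it requires only that progression come after next-line therapy started. Where the SAP wants an ordering condition it states one. The primary PFS censoring table (Table 4.1.2.1-1) counts a documented progression only if no subsequent anticancer therapy began earlier. The PFS2 steps have no such condition. Even if the narrower reading was intended, the text needs changing so that two programmers derive the same date.

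The points about reach do stand. Only one ordering of dates is affected, and the number of subjects is unknown. Differential switching by arm is a possibility, not something the documents show. No test, hazard ratio or p-value is listed for PFS2, so the effect would be on descriptive medians and curves. The planned listings of PFS and PFS2 and of follow-up therapy would help find affected subjects, although they would not correct the dates.

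**Conclusion.** The concern holds. As written, the SAP steps contradict the definition in both documents, and they err in one direction: PFS2 is too long by the interval from second next-line start to the recorded progression, for subjects in whom the former comes first. All other subjects are unaffected and event counts do not change. This rests on reading the first step literally and on progression dates still being recorded after a second next line has started. The total effect cannot be sized because the documents give no count of early switchers, and bias between arms is conditional on their differing in this respect. Since PFS2 is exploratory and carries no alpha, the point is minor.

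**What to change.** Replace the first two steps for subjects who received next-line therapy with one rule: the event date is the earliest of progression after next-line start, start of second next-line therapy, and death. Leave censoring at the date last known alive unchanged. This is one sentence in the SAP and one line of derivation code.

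There is one further cost. The document history says SAP version 5.0 was issued after the nivolumab-plus-chemotherapy interim, for which a study report was written. Appendix 5 carries forward an alpha of 0.035, which under Table 7.5.1-1 means both primary endpoints were positive (0.02 + 0.015). Section 10 then calls for a report with all SAP analyses, PFS2 included. The sponsor should count subjects in that report whose second next-line therapy preceded a recorded progression and, if there are any, re-derive their PFS2 so that both comparisons use the same rule. The corrected rule can be applied directly in the nivolumab-plus-ipilimumab report planned for the second analysis time point.

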### **4.3.2 Safety Exploratory Endpoints**

The assessment of safety will be based on the incidence of adverse events (AEs), serious adverse events (SAEs), adverse events leading to discontinuation, adverse events leading to dose modification, select adverse events (select AEs) for EU/ROW Submissions, immune-mediated AEs (IMAEs) for US Submission, other events of special interest (OEOSI), and deaths. The use of immune modulating concomitant medication will be also summarized. In addition, clinical laboratory tests, and immunogenicity (ie, development of anti-drug antibody) will be analyzed.

### **4.3.3 Outcomes Research Exploratory Endpoints**

#### **EQ-5D**

Subjects' reports of general health status will be measured using the EuroQoL EQ-5D-3L. EQ-5D-3L essentially has 2 components: the descriptive system and the visual analogue scale (VAS).

The instrument's descriptive system consists of 5 dimensions: mobility, self-care, usual activities, pain/discomfort, and anxiety/depression. Each dimension has 3 levels, reflecting "no health problems," "moderate health problems," and "extreme health problems." A dimension for which there are no problems is said to be at level 1, while a dimension for which there are extreme problems is said to be at level 3. Thus, the vectors 11111 and 33333 represent the best health state and the worst health state, respectively, described by the EQ-5D-3L. Altogether, the instrument describes  $3^5 = 243$  health states. Empirically derived weights can be applied to an individual's responses to the EQ-5D-3L descriptive system to generate an index measuring the value to society of his or her current health. Such preference-weighting systems have been developed for the UK, US, Spain, Germany, and numerous other populations. For this study, EQ-5D-3L utility index values will be computed using a scoring algorithm based on the United Kingdom Time-Trade-Off (UK TTO) value set.

In addition, the EQ-5D-3L includes a VAS, which allows respondents to rate their own current health on a 101-point scale ranging from 0="worst imaginable" health to 100="best imaginable" health state.

A change from baseline of 0.08 for the EQ-5D-3L utility index score and of 7 for the EQ-5D-3L VAS are considered minimally important differences for the EQ-5D-3L.

#### **FACT-Ga**

The FACT-Ga questionnaire and selected components, including the FACT-G7 and GaCS, will be used to assess the effects of underlying disease and its treatment on health-related quality of life (HRQoL) for patients.

As a generic cancer-related questionnaire, the FACT-Ga includes the 27-item FACT-General (FACT-G) to assess symptoms and treatment-related effects impacting physical well-being (PWB; seven items), social/family well-being (SWB; seven items), emotional well-being (EWB; six items), and functional well-being (FWB; seven items). Seven of these items comprise the FACT-G7, an abbreviated version of the FACT-G that provides a rapid assessment of general HRQoL in cancer patients.

In addition to the FACT-G, The FACT-Ga includes a 19-item disease-specific GaCS that assesses additional disease specific symptoms and impacts relating to pain, reflux, dysphagia, eating difficulties, tiredness, weakness, interference, and difficulty planning. Each FACT-Ga item is rated on a five-point scale ranging from 0 (not at all) to 4 (very much).

Scores for the PWB, FWB, SWB, and EWB subscales can be combined to produce a FACT-G total score, which provides an overall indicant of generic HRQoL. The FACT-G and GaCS scores can be combined to produce a total score for the FACT-Ga, which provides a composite measure

of general and targeted HRQoL. Higher scores indicate better HRQoL. The full FACT-Ga will be administered to subjects during the on-treatment phase and at follow up visits 1 and 2. However, to minimize subject response and administrative burden, only the FACT GaCS and FACT-G7 will be administered during the survival follow-up phase.

#### **4.3.4 Pharmacokinetics Exploratory Endpoints**

PK will be determined from serum nivolumab and ipilimumab concentrations. Samples will be collected to characterize pharmacokinetics of nivolumab and ipilimumab and to explore exposure-safety and exposure-efficacy relationships.

#### **4.3.5 Immunogenicity Exploratory Endpoints**

Serum samples collected will be analyzed by a validated immunogenicity assay. Selected serum samples may be analyzed by an exploratory orthogonal method that measures anti-nivolumab and anti-ipilimumab.

In addition, ad hoc serum samples designated for pharmacokinetic or biomarker assessments may also be used for immunogenicity analysis if required (eg, insufficient volume for complete immunogenicity assessment or to follow up on suspected immunogenicity related AE).

Immunogenicity endpoints are defined in [APPENDIX 3](#).

